6.5 Subject Withdrawal

For any subject who withdraws their consent following enrollment, the reason(s) for withdrawal will be documented on the appropriate CRF. In the event that a study subject does not finish their course of RT, the subject should be followed through 6 months from the date of the TraceIT hydrogel injection, whichever occurs sooner. For these subjects, participation will be concluded at that time and the subject will not participate in the longer-term toxicity assessment phase. Every attempt will be made to contact subjects who are non-compliant or lost to follow-up, and such attempts will be documented in the subject's study record.

Subjects may be replaced at the discretion of the Sponsor.

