6.4.2 Subject Enrollment

Prior to enrollment in the study, subjects will be evaluated to determine eligibility. The subject's willingness and ability to meet the follow-up requirements will be determined. If the subject desires to participate in the study, written informed consent will be obtained prior to performance of any study-specific examinations (see Section 6.4.3). Each subject will be assigned a screening number and will be entered on a screening log, which will be submitted regularly to the Sponsor. After the informed consent has been signed, a unique 5-digit subject identification number which includes the 2-digit site number plus a sequential 3-digit subject number starting at 001 (e.g., 01-001) will be assigned and subject is screened for eligibility criteria and considered enrolled in the study if all eligibility criteria is met. No two subjects will have the same five-digit subject identification number. This subject identification number will identify the subject throughout the study and will be used for all source documents and CRFs. Subjects who meet the eligibility criteria and agree to participate will be scheduled for TraceIT Tissue Spacer injection and fiducial marker placement.

A subject is considered enrolled in the study after the subject meets eligibility criteria. Only subjects who undergo TraceIT Tissue spacer injection attempt (i.e., at the time the needle is inserted through the duodenum) will be included in the safety/effectiveness populations for analysis. All subjects enrolled in the study will be required to adhere to the follow-up schedule outlined in this protocol. Subjects withdrawing consent after treatment will not be required to undergo follow-up after withdrawal; however, these participants will still be considered part of the study cohort and included in the safety analysis.

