7.7 Safety Analysis

Incidence of adverse events will be summarized by body system and preferred term in accordance with NCI Common Terminology Criteria for Adverse Events (CTCAE) v4.0 (NCI, Oct 2009) for severity and/or MedDRA term. The incidence of adverse events will be summarized by term, by term and procedure/device relationship, and by term and severity. All adverse events occurring at the time of initiation of fiducial marker placement or attempted injection and up through and including the 18 month visit will be recorded and listed. In addition to the general presentation of safety events, the following will be calculated and reported:

- The number and percentage of subjects who experience TraceIT administration procedure-related events which result in a delay in initiation of RT.

- The number and percentage of subjects with at least one duodenal adverse event presented by grade and timing; i.e., acute (within 3 months) and late (>3months). A similar presentation will be provided for non-resected subjects only.

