9.1.1 Recording and Reporting of Adverse Events

All study staff are responsible for ensuring that complete safety information has been recorded on the CRF and in source documents. All Adverse Events (AE) must be documented throughout the study. Medical assessments must be performed during each scheduled study visit and serve as the primary basis for identifying AEs. Although spontaneous or elicited medical complaints will likely constitute the majority of AEs, any non-scheduled visit to a healthcare provider or the initiation of a new medication should trigger additional questioning as to the occurrence of an AE.

All adverse events, regardless of severity or relationship to investigational device, will be collected from the time of initiation of fiducial marker placement and through the 18-month visit. Subjects who experience an adverse event related to TraceIT hydrogel will be followed until the adverse event has resolved or until the subject has stabilized and follow-up care has been transferred to the subject's primary care physician.

Any changes in a subject's condition noted prior to the procedure should be adequately assessed and included in the medical history for the subject.

Any event precipitating an intestinal acute CTCAE score of grade 2 or more must be documented as an adverse event.

To the extent possible, the event to be recorded and reported is the event **diagnosis** as opposed to event **symptoms**. Please refer to the following examples:

- Fever, chills, nausea and vomiting in the presence of a clinically diagnosed infection is to be reported as an infection only.
- Pain on urination in the presence of a clinically diagnosed urinary tract infection is to be reported as a urinary tract infection only.

Reporting Serious Adverse Events

All serious adverse events and serious adverse device effects shall be reported to the Sponsor or their representative (by fax or by phone) within 24 hours of the time the investigator learns of the event. A written report detailing the event and signed by the investigator shall be submitted to the Sponsor within 5 working days. The investigator shall notify the reviewing IRB of all serious adverse events occurring in the study according to the IRB's requirements.

Device failures or problems not associated with adverse events will be documented separately on the appropriate case report form. The product should be retained for evaluation.

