The following definitions will be used for Progression-Free Survival (PFS) and Overall Survival (OS) analysis:

- Progression-Free Survival (PFS): defined as the interval between the start of induction chemotherapy (prior to RT) to the earliest treatment failure (local, regional or distant progression) onset date or death (in months). Treatment failure events will be reported as SAE and adjudicated by CEC.
- Overall Survival (OS): defined as the interval between the start of induction chemotherapy (prior to RT) to death (in months).

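### Protocol 6.5 ends follow-up at 6 months for subjects who do not finish RT, leaving months 6 to 18 selectively unobserved for late toxicity, PFS and OS, and its time limit is incompletely written

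*Protocol*

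**What the plan says.** Protocol 6.5 has a separate rule for subjects who do not complete their RT course: "the subject should be followed through 6 months from the date of the TraceIT hydrogel injection, whichever occurs sooner." It continues: "For these subjects, participation will be concluded at that time and the subject will not participate in the longer-term toxicity assessment phase." The first sentence gives one date and nothing to compare it with. The section also states "Subjects may be replaced at the discretion of the Sponsor," and neither document says how a replaced subject is counted.

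Other sections describe 18 months of follow-up and do not mention this exit:

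- Protocol 6.4.2: "All subjects enrolled in the study will be required to adhere to the follow-up schedule outlined in this protocol."
- Protocol 9.1.1: adverse events are "collected from the time of initiation of fiducial marker placement and through the 18-month visit." Protocol 7.7 says that events "up through and including the 18 month visit will be recorded and listed."
- SAP 3.4 groups adverse events by onset since the index procedure. Its last two bands cover more than 6 to 12 months and more than 12 to 18 months.
- Protocol 7.7 and SAP 3.4.1 report the number and percentage of subjects with a duodenal adverse event, split into acute (within 3 months) and late (beyond 3 months).
- SAP 3.3 lists PFS and OS as exploratory. SAP 3.3.1 defines both as intervals from the start of induction chemotherapy and routes treatment failure through SAE reporting and committee adjudication.

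Neither document names an estimator or a censoring rule for PFS or OS. Missing outcome data are not imputed (Protocol 7.8, SAP 3.1.3).

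**The concern.** The exit is triggered by what happens to the subject after injection, not by withdrawal of consent. Toxicity, decline or progression are plausible reasons for not finishing RT. If they are the reasons, follow-up stops in the subjects whose later course is most informative about late duodenal injury, progression and death. An event caused by the injection procedure could itself contribute to RT not being finished, so device harm could shorten its own observation.

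Two features of the plan make the loss easy to overlook. The toxicity summary is a percentage of subjects, and no rule removes or flags a subject seen for only part of the window. Progression reaches PFS through SAE reporting, which has no planned route once participation has ended. The incomplete time limit adds a practical risk, because a site could read it as permitting a stop before 6 months.

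**Working it through.** The plan has no figure to reproduce: six subjects were chosen without a calculation (Protocol 7.1, SAP 3.1.2), and no non-completion, toxicity or survival rate is given. Non-completion rates, event risks and event times below are assumptions.

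**1. Late window observed.** Late means beyond 3 months, and collection runs to 18 months, so the window is 18 − 3 = 15 months. Exit at 6 months leaves 6 − 3 = 3 months, and 3/15 = 20%. With a constant hazard and a late-event risk p over the window, the share of late events seen by month 6 is [1 − (1 − p)^(3/15)]/p. This gives 21% at p = 0.15, 23% at p = 0.30 and 26% at p = 0.50.

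**2. Effect on the toxicity percentage.** With six subjects in the denominator, one late event that is seen gives 1/6 = 16.7% (exact 95% interval 0.4% to 64.1%). If it is missed, the result is 0/6 = 0% (0% to 45.9%). The intervals are added here for scale; the plan does not call for them on this outcome.

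**3. Chance that the rule is used.** P(at least one non-finisher among six) = 1 − (1 − q)^6.

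| Assumed non-completion rate q | 5% | 10% | 15% | 20% | 30% |
|---|---|---|---|---|---|
| P(at least one) | 26% | 47% | 62% | 74% | 88% |

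**4. OS, if it were summarised by Kaplan-Meier.** Time runs from the index procedure. Assume k non-finishers, all dying at month 9, and d deaths among the other 6 − k subjects (at month 12 if d = 1; at months 10 and 14 if d = 2). Everyone else is alive at 18 months.

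- Exit at 6 months: S(18) = (6 − k − d)/(6 − k)
- Full follow-up: S(18) = (6 − k − d)/6

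| k | d | Exit at 6 months | Full follow-up | Overstatement (points) |
|---|---|---|---|---|
| 1 | 0 | 5/5 = 100% | 5/6 = 83% | 17 |
| 1 | 1 | 4/5 = 80% | 4/6 = 67% | 13 |
| 1 | 2 | 3/5 = 60% | 3/6 = 50% | 10 |
| 2 | 0 | 4/4 = 100% | 4/6 = 67% | 33 |
| 2 | 1 | 3/4 = 75% | 3/6 = 50% | 25 |
| 2 | 2 | 2/4 = 50% | 2/6 = 33% | 17 |

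The direction depends on the assumption. If the single non-finisher with d = 1 were instead alive at 18 months, full follow-up would give 5/6 = 83% against 4/5 = 80%, a small understatement. A death before month 6 is captured either way.

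**5. What is not touched.** Technical Success is read on the post-injection CT. The plan comparison uses planning done less than 28 days after the procedure (Protocol 6.4.8). The RT-delay endpoint concerns the start of RT. All three are settled before month 6.

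**The case against.** The strongest reply is that Protocol 6.5 is a deliberate exception. The schedule that Protocol 6.4.2 refers to is the one in this protocol, which includes 6.5, and non-injection subjects likewise have a shorter follow-up (6.4.7). Protocol 5 makes the 6-month visit the end of device-safety assessment, and Table 2 marks it as the end of the regulatory phase. Protocol 4.1 says the hydrogel degrades within 7 months, and 9.1.1 follows hydrogel-related events until resolution or stabilisation. Early terminations are reported with reasons (Protocol 7.5, SAP 5.1.1), and with six subjects and full listings an exit would be visible. The affected outcomes are exploratory or descriptive, and any 18-month survival figure from six subjects is very imprecise.

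Much of this stands and limits the importance of the point. The conflict with 6.4.2 can be read as an exception lacking a cross-reference. However, following an event to resolution covers events already begun, not new ones. Ending the device-safety assessment at month 6 does not explain why the SAP goes on to report adverse events to 18 months and survival through follow-up. Eligibility requires a life expectancy of at least 9 months (Protocol 6.3.1), so deaths after the exit date are to be expected.

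A reader might infer that the plan builds in informative censoring of late toxicity, PFS and OS. The documents do not support that. Late toxicity is a crude percentage, so the problem there is under-ascertainment, with months 3 to 6 still observed. For PFS and OS no censoring rule or Kaplan-Meier method is specified, so the handling is undefined.

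**Conclusion.** The point holds as a gap in follow-up and an incomplete clause; it does not threaten the main conclusions. Protocol 6.5 needs to be reconciled with the 18-month collection and reporting in Protocol 7.7 and 9.1.1 and SAP 3.4, and its time limit needs a second date or none.

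For each affected subject, 12 of the 15 late-window months go unobserved. A single missed late event moves the toxicity result by one sixth. The 10 to 33 point overstatement of 18-month OS rests on three assumptions: one or two non-finishers, all dying after exit and before 18 months; a Kaplan-Meier summary; and time counted from the index procedure, not from induction chemotherapy as the plan defines OS. It illustrates sensitivity and does not predict the trial's result.

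It is tempting to state as fact that non-finishers are those most likely to have toxicity or progression. That is a reasonable assumption, but neither document gives rates of, or reasons for, non-completion.

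**What to change.** 1. In Protocol 6.5, delete the early-exit sentence as far as data collection is concerned. Continue to collect adverse events, known progression and vital status to Month 18 from every injected subject who has not withdrawn consent, whether or not RT was completed. A visit, the medical record or a telephone call would serve.
2. Delete the closing qualifier on the 6-month limit, or name the second date it refers to.
3. In the SAP, state the censoring rule and summary method for PFS and OS, and report the follow-up actually observed beside the late-toxicity percentage. Say also how replaced subjects are counted.

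The cost is a short amendment and at most two further contacts per affected subject, at Months 12 and 18, which the protocol summary already places within standard of care. One limit remains: no imaging is scheduled for anyone after the Month 6 MRI, so progression after that point will still depend on standard-of-care records.

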7 STATISTICAL ANALYSIS

7.1 Sample Size Determination

No formal hypothesis or sample size estimation has been established since this is an early feasibility study with an intent to collect information concerning the procedural characteristics and safety for TraceIT administration within the peri-duodenal space. Six (6) subjects should provide sufficient experience to allow for evaluation of procedural safety and to estimate the impact of space creation on duodenal radiation doses.

7.2 General

The statistical analysis of the data obtained from this study will be performed using SAS[®] Version 9.3 or higher.

All data collected in this study will be documented using summary tables and subject data listings. Continuous variables will be summarized using descriptive statistics, specifically the mean, median, standard deviation, minimum and maximum. Categorical variables will be summarized by frequencies and percentages.

Changes from baseline in dosimetric parameters and quality of life parameters will be assessed using a paired t-test or, if not normally distributed, the nonparametric Wilcoxon Signed-Rank test for continuous variables and Chi-Square and/or McNemar's test for dichotomous variables. Nominal p-values associated with statistical tests will be reported, but no significance level will be assigned to the values. No adjustments to nominal p-values are planned since this is a hypothesis-generating study.

A detailed statistical analysis plan will be developed and finalized prior to database lock.

7.3 Analysis Populations

7.3.1 Intent-to-Treat Population (ITT)

All enrolled (consented) subjects for whom TraceIT administration is attempted. This will be the primary analysis population for evaluation of feasibility (i.e., technical success defined as the ability to place TraceIT and create space between the duodenum and HOP).

7.3.2 Modified Intent-to-Treat Population (MITT)

All subjects enrolled in the study and who are a Technical Success will be included in the Modified Intent-to-Treat population. This will be the primary analysis population for purposes of non-safety outcome data.

7.3.3 Per Protocol Population

The Per Protocol (PP) Population is defined to be all subjects in the MITT population with no major protocol deviations that have the potential to affect the study outcomes.

7.3.4 No TraceIT Population

Subjects who were enrolled (consented) and for whom TraceIT administration was not technically successful (either hydrogel placement was abandoned due to clinical issues or no space created in the duodenal/pancreatic interface).

7.3.5 Safety Population

The Safety Population is defined to be all subjects for whom TraceIT administration is attempted (whether or not administration was successful). For the purposes of this study, the Safety Population is the same as the ITT Population.

7.4 Subgroup Analyses

Data may be presented separately for localized (resectable, BRPC and LAPC) subjects as well as resected and unresected subjects. Details will be provided in the statistical analysis plan.

7.5 Subject Disposition

The number and percentage of enrolled (ITT Population), MITT, PP and Safety Populations will be summarized. The number of subjects signing the informed consent and the number of primary screening failures (consented but not treated subjects) and the number of secondary screening failures (Duodenal invasion seen at time of index procedure) will be presented. The number and percentage of non-injection TraceIT subjects will be presented along with the reason they were not able to be injected. The number and percentage of treated subjects who do not complete the study will be presented, along with the reason for early termination/withdrawal. Subject accountability by investigative site and by study visit will also be presented.

7.6 Planned Analyses

7.6.1 Baseline Characteristics

Subjects will be summarized with respect to baseline demographics and clinical characteristics (e.g., age, sex, tumor grade, etc.). These will be summarized by descriptive statistics including means, medians, standard deviations and ranges (for quantitative variables) and percentages (for categorical variables).

7.6.2 Technical Success, TraceIT Injection and Device Use

Summary statistics will be presented for characteristics of TraceIT injection using descriptive statistics or counts and percentages, as appropriate. In addition, the proportion of TraceIT treated subjects in whom Technical Success has been achieved will be reported, together with an exact (Clopper-Pearson) 95% confidence interval for the true proportion. Technical Success is defined as the administration and visualization (on post-injection CT) of the TraceIT hydrogel between the head of pancreas and the duodenum.

Ease of device use and preparation, and whether any device malfunctions occurred will be summarized by counts and percentages. Details of device malfunctions will be presented in a listing.

7.6.3 Radiotherapy Benefits

Treatment planning will be performed as a component of the Baseline Assessment and repeated following TraceIT administration. For both scans, summary descriptive statistics will be presented by assessment (i.e., Pre vs. Post TraceIT Administration) for all target volume and dose constraint measurements. For the post-TraceIT procedure data, the relative reduction from baseline in dose (V15, V20, V35, mean and maximum duodenal dose, etc.) to the duodenum will also be calculated and summarized. For continuous variables, the paired sample t-test will be used to test for a difference in means between treatment plans.

7.6.4 Change in Baseline in Quality of Life Measures

Changes in Quality of Life Measures as assessed overall and subdomains of the EORTC-QLQ-C30 and QLQ-PAN26 will be evaluated. Raw scores and change from baseline scores will be calculated for all domains. Scores will be compared to baseline using either a paired t-test or Wilcoxon Signed-Rank test.

7.6.5 Other Outcome Measures

All other measures as identified in Section 6.1.3 not described above will be evaluated in accordance with the general statistical methods previously identified. The following definitions will be used for PFS and OS:

- Progression-Free Survival (PFS): defined as the interval between the start of induction chemotherapy (prior to RT) to treatment failure (local, regional or distant progression) or death (in months).
- Overall Survival (OS): defined as the interval between the start of induction chemotherapy (prior to RT) to death (in months).

7.7 Safety Analysis

Incidence of adverse events will be summarized by body system and preferred term in accordance with NCI Common Terminology Criteria for Adverse Events (CTCAE) v4.0 (NCI, Oct 2009) for severity and/or MedDRA term. The incidence of adverse events will be summarized by term, by term and procedure/device relationship, and by term and severity. All adverse events occurring at the time of initiation of fiducial marker placement or attempted injection and up through and including the 18 month visit will be recorded and listed. In addition to the general presentation of safety events, the following will be calculated and reported:

- The number and percentage of subjects who experience TraceIT administration procedure-related events which result in a delay in initiation of RT.

- The number and percentage of subjects with at least one duodenal adverse event presented by grade and timing; i.e., acute (within 3 months) and late (>3months). A similar presentation will be provided for non-resected subjects only.

7.8 Incomplete/Missing data

All practical monitoring and follow-up steps will be taken to ensure complete and accurate data collection. Due to the fact that subjects are undergoing therapy consistent with standard medical practices, it is anticipated that there will be minimal missing data. There will be no imputation of missing data.

8 RISK/BENEFIT ANALYSIS

8.1 Risk/ Benefit Analysis

Radiation therapy is a common component of treatment for pancreatic cancer. However, due to the pancreas' anatomic proximity to the duodenum, duodenal radiation injury is a risk of radiotherapy. Indeed, when delivering stereotactic doses of radiation in multiple fractions, as is the current convention, and when adhering to contemporary duodenal dose constraints, the rates of medically significant grade ≥ 3 duodenal toxicity continues to be a problem reported in up to 15% of patients¹⁷. Since the risk of developing duodenal complications increases exponentially as greater volumes are irradiated, it is understandable that clinicians are seeking technologies that can reduce duodenal radiation dose to minimize the risk of duodenal injury associated with radiation therapy and maximize the tumor coverage.

Based upon the results of the preclinical investigations and validated through clinical use, PEG-based hydrogels have been shown to be safe in multiple tissue types including sensitive neurological and intra-abdominal tissues. The transduodenal injection procedure used for administration of the TraceIT hydrogel is commonly performed by endoscopists for the performance of pancreatic biopsies and the delivery of fiducial markers. Moreover, Augmenix in conjunction with researchers at John Hopkins Medical Center has performed a cadaver study demonstrating that creation of space between the duodenum and pancreas can substantially reduce the level of duodenal radiation exposure while maintaining or in some cases even improving PTV coverage, having a positive impact for both the reduction in duodenal toxicity and maximizing effects of RT on the tumor. Conversely, there is no information in the preclinical data to suggest that the hydrogel material or the methods used for administration present the potential for significant harm when used as intended.

Therefore, TraceIT hydrogel when used to displace the duodenum from the pancreas may provide a substantial clinical benefit as a duodenal-sparing technology that allows for a reduction in duodenal radiation dose and improvement in PTV coverage in patients undergoing radiotherapy for pancreatic cancer. It is acknowledged, however, that as with any medical procedure and implanted material there are risks associated with the use and administration of the TraceIT hydrogel. Based on the clinical knowledge for the device's application and preclinical study outcomes, potential risks associated with the hydrogel have been identified (outlined below). Risks have been mitigated to the extent possible, providing a favorable risk/benefit profile for the TraceIT Tissue Spacer.

